1. BACKGROUND AND SIGNIFICANCE

1.1. Postpartum depression. [Note: Although postpartum depression is a time-honored diagnosis, the DSM-5 lists the diagnosis Peripartum Depression instead, in recognition of cases in which depression may have its onset even *prior to* parturition. However, because the focus of this proposal is the prevention of depressive symptoms *following* parturition, we will use the term postpartum depression (PPD) throughout this proposal.] PPD is a debilitating disorder. New mothers must struggle with the adverse consequences of depression and at the same time be responsible for parenting their child. PPD poses a threat to mother *and* infant health, which in extreme cases may involve maternal suicide and/or infanticide. An estimated 600,000 American women suffer from PPD annually, making it one of the most frequent complications of pregnancy. Available secondary preventive interventions often are ineffective, which calls for identifying novel approaches (O’Hara and McCabe, 2013).

Impaired infant-mother bonding is a hallmark of PPD (O’Higgins et al., 2013). Depressed mothers have more difficulties developing maternal feelings towards their infant and are less likely to provide sensitive caregiving, providing fewer opportunities for reciprocal engagement. In turn, bonding impairments may worsen the mother’s depression, creating a vicious cycle. Resultant disruptions in the early mother–infant relationship may engender insecure attachment, with consequent lifelong disruptions in the child’s socioemotional and cognitive development.

1.2. Postpartum posttraumatic stress disorder (PP-PTSD). Posttraumatic stress symptoms have also been described in mothers following a traumatic childbirth experience, and these may overlap with PPD (Söderquist et al., 2009), creating further maternal morbidity as well as

diminishing mother-infant bonding (Parfitt and Ayers, 2009). As our study and others show, women who develop PP-PTSD are also at risk for suffering from bonding impairment (Dekel et al., 2018) and interruption in the mother-infant bonding relationship in the sensitive postpartum period which can adversely modify the child's developmental trajectory.

1.3. Current treatment status. Antidepressant medication is the most common treatment for PPD and also for PP-PTSD, although there is no evidence that antidepressant perform better than placebo and women who breastfeed are ambivalent about taking the drug (O'Hara and McCabe, 2013). There is no treatment that specifically targets PP-PTSD (Olde et al., 2006). Moreover, antidepressant has not been found to help with bonding impairments. Antidepressants do not prevent PP-PTSD (Dekel et al., 2016). To date there are two direct interventions to promote bonding, viz., baby massage and coaching; both are partially effective at best. There is a need for a brief, inexpensive, feasible treatment to enhance bonding. Here we propose a novel intervention aimed at enhancing maternal bonding, and reducing PPD and posttraumatic symptom severity. We will test the heretofore uninvestigated clinical preventive potential of the posterior pituitary peptide hormone *oxytocin* (OXT), administered intranasally (IN), to mothers during the first postpartum days.

1.4. Theoretical basis for administering oxytocin. In addition to IN-OXT's putative anxiolytic and antidepressant properties (Bakermans-Kranenburg and van IJzendoorn, 2013), a large body of research supports OXT's role in the maintenance of maternal behavior across species. OXT knockout mice display deficits in maternal behavior, and exogenous administration of OXT enhances it. Recent evidence in postpartum mothers indicates that high peripartum OXT levels are associated with enhanced maternal behavior (Feldman et al., 2007), and low levels with depressive symptoms (Skrundz et al., 2011). Low OXT levels during bonding have been documented in depressed women (Stuebe et al., 2013), suggesting that OXT deficiency is an underlying mechanism of impaired bonding in PPD. Exogenous OXT administration has been found to enhance maternal brain responses in women (Riem et al., 2011), as well as to reduce the fear response in healthy humans (Acheson et al., 2013), suggesting it may also be a promising candidate for PP-PTSD. In a non-postpartum sample, IN OXT given to individuals at risk for PTSD following trauma exposure shows beneficial effects of the treatment in lowering non-postpartum PTSD (van Zuiden et al., 2017). Abnormalities in the biological stress response manifested in dysregulations in the hypothalamic-pituitary-adrenal (HPA) axis is a hallmark of PTSD. OXT deficiency may heighten the stress response in humans (Donadon et al., 2018) in part through failure to reestablish bodily homeostasis following exposure to the trauma. Low OXT after traumatic exposure has been documented in individuals with PTSD. OXT production peaks in labor (Fuchs et al., 2016), as is the norm, and has been associated with extinction of the memory for the traumatic nature of the birth experience (Brindle et al., 1991; Brett and Baxendale, 2001). This accords with OXT's specific role in reducing traumatic memory overconsolidation to protect against PTSD. Thus, increase of OXT in the immediate postpartum may protect women following a traumatic delivery.

1.5. Intranasal oxytocin and brain access. For exogenous OXT to enhance bonding it must exert effects on the central nervous system (CNS) through brain OXT receptors. IN administration of OXT has been found to produce significantly increased OXT levels in cerebrospinal fluid (CSF) after IN delivery (Striepens et al., 2013). Side effects were not

observed after the delivery of short-term 18 to 40 IU IN-OXT to humans (MacDonald et al., 2011), including postpartum women (Rupp et al., 2014). Of direct relevance to the proposed project, a study that investigated the role of sequential IN-OXT in promoting lactation at a dose of 4 IU in each nostril q 4h (total daily dose 48 IU), from as early as one day postpartum, found no safety concerns (e.g., Fewtrell et al., 2006). Administration of OXT was documented to reduce the fear response in healthy humans (Acheson et al., 2013). In an animal model, central OXT administration in the immediate post-stressor phase reduced PTSD-like behavior (Cohen et al., 2010). A few studies support of the use of OXT to facilitate fear extinction in the treatment of individuals suffering from PTSD (Koch et al., 2014; Koch et al., 2016). However, given the unpredictable nature of traumatic events, designing prospective studies to test OXT's protective role is challenging. A recent study of sequential IN-OXT administration *after* (day 12) an automobile accident shows some beneficial effects for PTSD reduction (van Zuiden et al., 2016). Along these lines, it is suggested that there might be a "window of opportunity" for a preventive intervention in the *first days* following traumatic exposure, viz, before the trauma memory is consolidated and symptoms arise (Zohar et al., 2011).

1.6. Significance of the study. Our study will attempt to fill the current gap in effective preventive interventions for pregnant mothers at risk. No study has yet examined the therapeutic effects of OXT on maternal bonding as well as on early PPD and PP-PTSD symptoms. If we succeed in establishing the effectiveness of this highly feasible preventive intervention, it could become a stand-alone treatment for bonding impairment. Our intervention may also offer hope for women at risk for the aversive complications of childbirth-related psychopathology. Strengthening the important process of mother-infant bonding from the very beginning of the child's life may also have long-lasting positive implications of the child's psychological development. We further expect that our findings will advance the scientific knowledge concerning the major role of OXT in social interaction, and its anti-anxiety and anti-depressive properties in humans. Research on the clinical potential of IN-OXT for treating mental illness, although promising, is in its infancy, and our study may provide knowledge concerning issues of dosage and timing in order to achieve sustained central nervous system effects. Lastly, our findings may revise central concepts in postpartum psychopathology. Obtaining data that attribute PPD to a bonding impairment, and the prevention of PPD by enhancing bonding, may challenge the current psychiatric conceptualization of PPD as merely a subtype of depression. Implication of posttraumatic stress symptoms in PPD may shift the focus of postpartum mental health to include traumatic stress responses. Evidence of sustained OXT effects on bonding may provide empirical support in favor of a sensitive period for mother-infant bonding in the early postpartum period, which would have important health care implications.

2. SPECIFIC AIM

2.1. The primary hypothesis is that administration of a course of four days of IN-OXT at a dose of 4 IU in each nostril q 4h (total daily dose 48 IU), from as early as one day postpartum, initiated immediately following delivery, in comparison to placebo (PLA), will: 1) enhance mother-infant bonding, and 2) reduce PPD and PP-PTSD symptoms, at 5 days and again at two months postpartum, in mothers at risk for bonding failure and PPD.

2.2. We further hypothesize that bonding level will mediate the hypothesized beneficial effect of IN-OXT on depressive symptoms. Secondarily, we also hypothesize that IN-OXT will have positive effects on breastfeeding, and that improved breastfeeding will improve depression.

3. SUBJECT SELECTION

For Oxytocin study

3.1. Inclusion Criteria. 1) Third-trimester pregnant women being followed at the MGH Obstetrics Program who are at risk of PPD as indicated by their scoring >9 on a prenatal administration of the Edinburgh Postnatal Depression Scale (EPDS). (Note: Although the adjective “Postnatal” refers to the use of the EPDS during the *postpartum* period, this instrument is also used as a *prepartum* screening instrument for PPD risk.) Additionally, we will enroll women with score of >21 on the Peritraumatic Distress Inventory (PDI) who might also be at risk for bonding impairment from PPD and PP-PTSD.

3.2. Exclusion criteria. 1) Age <18 or >50; 2) Failure to participate in regular prenatal check-ups; 3) Current diagnosis of psychosis; 4) Obstetric complication (e.g., preeclampsia, excessive hemorrhaging, gestational diabetes insipidus, emergency Caesarian section resulting in the newborn being admitted to the NICU). Note that planned Caesarian section will not serve as an exclusion criterion because immediate contact with the newborn occurs after the procedure.); 5) Use of potentially confounding or interacting medications (e.g. antidiuretic hormone, steroids); 6) Complicating pediatric medical condition in the newborn.; 7) suicidality (candidates indicating 2+ on EPDS item 10 will be further assessed by PI, a licensed clinical psychologist); 8) current substance abuse.

3.3. Recruitment methods. 3596 women delivered a baby at Massachusetts General Hospital (MGH) in 2012. During proposed five-year project period, we plan to recruit 110 subjects (Sbj's) (who satisfy the inclusion and exclusion criteria) and expect a drop-out rate of 20% between assessments, resulting in an anticipated final sample of 56 women. Additionally, we plan to recruit and study 88 partners (starting at day 1 postpartum, taking into account women's drop-out rate between pre-partum and day 1 postpartum assessments), also expecting a drop-out rate of 20% between assessments, resulting in a final sample of 56 partners.

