5. STUDY PROCEDURES

5.1. Design.

Phase I: Screening (two stages).

First, study candidates (third trimester of pregnancy) will undergo screening via self-report questionnaire, the EPDS, to identify women at risk for PPD. Next, study candidates will be further screened over the telephone or in person at the OB by a study staff. For exclusion criteria, use of potentially confounding or interacting medications (e.g. antidiuretic hormone, steroids), and current mental disorders assessed by the mini Structural Clinical Interview for DSM (mini SCID). The treating obstetrician will be asked regarding contraindicating medical conditions (e.g., preeclampsia). Also, candidates' medical records will be reviewed for exclusion criteria. For those who will be enrolled from the Mothers Wellbeing Study, we will enroll them based on their PDI score obtained as part of the Mothers Wellbeing Study. Medical records will be reviewed for exclusion.

Phase II: Assessment. i) At *approximately 32 weeks of pregnancy*, study Sbj will complete additional self-report questionnaires and 40 mL of blood will be collected from Sbj, if she agrees. ii) *Postpartum (PP) Day 1*, Sbj will complete further self-report questionnaires. *Starting 8 hours after delivery with modification in the start time up to 12 hours postpartum if needed*, Sbj will self-administer the first dose of study medication in the hospital. In cases of delays due to medical procedures (e.g., emergency C-section) medication start time will be extended to up to 24 hours post-delivery. iii) *PP Days 1-4*, Sbj will continue to self-administer the medication in the hospital and then at home. iv) *Approximately PP Day 5*, Sbj will complete additional self-report questionnaires. v) *2 months, but with modification up to approximately 3 months PP*, Sbj will complete the same self-report measures and participate in a short video-clip with her infant. 40 mL of blood will be collected from Sbj, if she agrees. Following this, PI will answer any questions Sbj may have and make mental health treatment referral, if indicated and desired. Women enrolled through the Mothers Wellbeing Study will begin this study at PP Day 1.

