Multidimensional Scale of Perceived Social Support [MSPSS]), trauma history (Life Events Checklist for DSM-5 [LEC-5], Childhood Trauma Questionnaire Short Form [CTQSF]), sleep (Bergen Insomnia Scale [BIS]), and expectations about delivery (Wijma Delivery Expectancy/Experience Questionnaire [W-DEQ 1]). All study questionnaires will be completed electronically, with the option to complete hard copies. If needed, self-report measures may be completed remotely. Following this, Sbj will be taught to self-administer the nasal spray containing either drug or placebo. Finally, if agreed by Sbj, 40 mL of blood will be collected from Sbj from venipuncture specimens performed for the purpose of this study and related studies. Samples will be later analyzed for hormone levels (e.g., oxytocin and cortisol) and DNA. Sbj (and her partner, if involved) will be contacted approximately 1 month after Assessment 1 as a reminder about her participation in the study.

5.1.2. Assessment # 2 and initial study medication administration (approximately 8 hours after delivery). Study staff will receive epic notification indicating that Sbj has been admitted to the Labor and Delivery Unit (L&D). Sbj will complete questionnaires (25 minutes total) at MGH's postpartum unit targeting mental health (BSI), peritraumatic responses (Peritraumatic Dissociative Experiences Questionnaire [PDEQ], Peritraumatic Distress Inventory [PDI], [W-DEQ 2]), depressive symptoms [EPDS], maternal bonding (Mother-to-Infant Bonding Scale [MIBS], and medication (MED). Additionally, as prescribed in the physicians order sheet (OXT order sheet), Sbj will self-administer the study medication (Syntocinon 40 mg/ml or placebo nasal spray, per randomization schedule), 1 spray into each nostril, before feeding their baby if possible, q 4 hours, including nighttime.

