6. BIOSTATISTICAL ANALYSIS

6.1. Statistical analysis will be performed via a mixed model for repeated measures, with Drug (OXT vs. PLA) as a Class factor, psychometric scores as univariate and/or simultaneous multivariate dependent measures, additional covariates as appropriate, and Sbj as a random effect. Currently available mixed model analytic programs are able to handle missing data. Effect sizes will be employed in power analyses to calculate sample sizes for subsequent larger studies. Path analysis will be employed to test the role of bonding as a mediating factor of drug effect on depression outcome.

6.2. Power analysis. The major goal of this first study is to obtain measures of effect size that can be used to calculate sample size requirements for a subsequent, larger study, should the data from this study be promising. Thus, even if we are unable to meet the recruitment goals below, the study will still obtain useful and important data. That being said, we offer the following power analysis below, should recruitment go as well as hoped.

Because of the novelty of this project's hypothesis, no data are available regarding the potential protective effect of IN-OXT against the development of PPD, from which to estimate an effect size for the proposed study. However, a meta-analysis of studies of the effect of intranasal OXT in both healthy and clinical groups with implications for pharmacotherapy yielded an estimated effect size of $d=0.32$ (Bakermans-Kranenburg and van IJzendoorn, 2013), on which we will base our power analysis. With α set at 0.05, and $1-\beta$ (i.e., power) set at 0.80, $n=56$ Sbjs (approximately 28 completed Sbjs in each of two groups) will be required to detect an effect size of $d=0.32$ in a simple t-test analysis comparing OXT and PLA subjects. Estimating dropouts at 20% between assessments, 70 and 88 Sbjs and partners will have to complete the second and first postpartum assessments, respectively, and 110 Sbjs will be required to complete the pre-partum assessment. Of all pre-partum women given psychometrics, an estimated 20% will be found to be at-risk, requiring the administration of psychometrics to 550 study candidates. To summarize:

550 administered psychometrics

110 women identified at risk, pass final screening, and complete pre-partum assessment
88 women randomized, and complete assessment #2; 88 partners complete assessment #1 at day 1 postpartum

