NCT02505984

Preventing Postpartum Depression with Intranasal Oxytocin

Date of document: 12/27/2024

Data Analysis

The final sample size includes 38 eligible women randomly assigned to oxytocin administration ($n = 18$) or placebo ($n = 20$). Missing data were allowed such that 18.59% of the data were missing, with 23 different patterns. Jamshidian and Jalal's non-parametric Missing Completely At Random (MCAR) test indicated that the data was Missing At Random (MAR): Hawkins's test, $\chi^2_{\text{median}(6)} = 14.33$, $p_{\text{median}} = .026$, and Anderson-Darlin's rank test, $T_{\text{median}} = 5.88$, $p_{\text{median}} = .005$. Missing data was handled by Multiple Imputation (Rubin, 2009) with 50 complete sets. The reported basic results are the pooled outcome of the MI procedure. Before the primary analyses, we examined the normal distribution of all the quantitative study measures using a series of Anderson-Darling normality tests. Basic analyses for study group comparison on outcome measures for each time point were performed using Mann-Whitney U tests.

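### The SAP's stated arm comparison uses neither entry route nor the Day 1 scores, which costs precision and protection against an observed imbalance

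*Protocol*

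**What the plan says.** Protocol section 3.1 gives two ways into the trial. The first is a third-trimester woman "scoring >9 on a prenatal administration of the Edinburgh Postnatal Depression Scale (EPDS"). The second is added in the same paragraph: "we will enroll women with score of >21 on the Peritraumatic Distress Inventory (PDI"). Section 5.1 says of women coming from the Mothers Wellbeing Study that "we will enroll them based on their PDI score obtained as part of the Mothers Wellbeing Study", and adds: "Women enrolled through the Mothers Wellbeing Study will begin this study at PP Day 1". These women therefore enter after the pre-partum visit (Assessment 1, section 5.1.1).

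The first visit common to both routes is Assessment 2 on Day 1 (section 5.1.2). It collects EPDS, MIBS, BSI and PDI, among others, but not PCL-5 or PBQ.

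The only description of allocation is "placebo nasal spray, per randomization schedule" (section 5.1.2), with no method, blocks or strata. The protocol's model (section 6.1) is a repeated-measures mixed model with Drug as a factor, "additional covariates as appropriate, and Sbj as a random effect"; no covariate is named. The SAP states: "Basic analyses for study group comparison on outcome measures for each time point were performed using Mann-Whitney U tests". It reports 38 women (18 oxytocin, 20 placebo), 18.59% missing data and 50 imputed sets. It does not mention entry route and does not list the imputed variables.

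**The concern.** One group is chosen for depressive symptoms in pregnancy, the other for distress around delivery. It is plausible that they differ in later EPDS and PCL-5 scores, though the documents give no figure. With arms of 18 and 20, the routes may split unevenly by chance. A Mann-Whitney test has no place for a covariate, so any such split passes straight into the arm difference. The same test also sets aside the Day 1 scores, which are the most obvious source of extra precision.

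This matters because Protocol section 6.2 makes effect-size estimates for a larger trial the main goal. Once a particular imbalance has occurred, the unadjusted estimate is off by that imbalance times the route difference, and the error carries into the next sample size. Readers could not detect it, since counts by route and arm are not reported.

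Entry route is also a known design reason for having no Assessment 1 data. An imputation that relies on data being missing at random should condition on it if those scales are used.

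**Working it through.** **Inputs from the documents.** Arms of 18 and 20 (SAP); planned effect d=0.32 and about 28 completers per arm (Protocol 6.2). **Assumed, because not given:** PDI share 10-50%; outcome difference between routes 0.25-1.0 SD.

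**Step 1: the plan's own figure.** Section 6.2 says 56 women give 80% power for d=0.32. A two-sided t-test needs 2 × (1.96 + 0.84)² / 0.32² ≈ 154 per arm (normal approximation), so the figure does not reproduce. Power is about 22% at 28 per arm and 16% at 18/20. That is a separate problem; d=0.32 serves below only as a yardstick.

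**Step 2: chance imbalance at 18/20.** If allocation was not stratified, and K of the 38 women entered by PDI (p = K/38), the SD of the difference in PDI share between arms is sqrt[p(1−p) × (38/37) × (1/18 + 1/20)]. The shift in the arm difference is the imbalance times the route difference. For routes 0.5 SD apart, with 95th percentiles from the exact hypergeometric distribution:

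| Assumed share (K of 38) | SD of share difference | Typical (1 SD) shift | 95th percentile of absolute shift |
|---|---|---|---|
| 10% (4) | 0.101 | 0.051 SD = 16% of 0.32 | 0.100 SD = 31% |
| 20% (8) | 0.134 | 0.067 SD = 21% | 0.117 SD = 36% |
| 30% (11) | 0.149 | 0.075 SD = 23% | 0.147 SD = 46% |
| 50% (19) | 0.165 | 0.082 SD = 26% | 0.158 SD = 49% |

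The simple formula 1.96 × sqrt[p(1−p)(1/18 + 1/20)] × 0.5 agrees: 0.10-0.16 SD, or 30-50% of 0.32.

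**Step 3: sensitivity to the route difference.** At 0.25 SD the typical shift is 8-13% of 0.32 and the 95th percentile 16-25%. At 1.0 SD they are 32-51% and 62-99%. The chance of a shift of at least half the planned effect (0.16 SD) is 0-3% for routes 0.5 SD apart and 11-33% for routes 1.0 SD apart.

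**Step 4: against total sampling error.** The standard error of the unadjusted difference is sqrt(1/18 + 1/20) = 0.325 SD, or 102% of 0.32. The shifts above are one component of it, not an addition to it.

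**Step 5: what adjustment buys.** Route explains p(1−p) × 0.5² of the outcome variance: 0.09 × 0.25 = 2% at a 10% share and 0.25 × 0.25 = 6% at 50%. The standard error falls from 0.325 to 0.321-0.315. At 28 per arm with a 30% share, power moves from 21.7% to 22.7%. A Day 1 score can do more. If its correlation with the outcome is r (assumed), the standard error becomes 0.325 × sqrt(1−r²): 0.310 at r=0.3, 0.281 at r=0.5 and 0.260 at r=0.6. The number per arm for 80% power at d=0.32 falls from 154 to 140, 115 and 99. The degree of freedom used is ignored here.

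**The case against.** A reader might infer four stronger things, and the documents support none of them.

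- **That randomisation ignored route.** The schedule is undescribed. It may have been stratified, in which case most of step 2 falls away.
- **That the drug effect is biased, or type I error inflated.** Chance imbalance under randomisation is already in the unadjusted standard error. What stands is the conditional point: after an imbalance has been observed, the unadjusted estimate is off in a direction that adjustment would correct.
- **That no adjusted analysis was planned.** The protocol's model leaves covariates open, and the SAP calls the Mann-Whitney tests basic and refers separately to primary analyses. But it does not describe those analyses, so the rank test is the only arm comparison it states.
- **That pre-partum scores were imputed for women who never had that visit.** The SAP does not list the imputed variables, so this remains conditional.

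Two further objections carry weight. The documents do not show that any of the 38 women entered by PDI: section 4 describes enrolment through the EPDS, and the recruitment figures in section 6.2 count only prenatal screening. And the sample size is the larger weakness, which adjusting for route hardly touches. Neither removes the case for using the Day 1 scores, which does not depend on the PDI share.

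**Conclusion.** The point holds in a limited form. Two differently selected groups are pooled, neither document names route as a stratum or covariate, and the SAP's stated comparison uses neither route nor the Day 1 scores. The cost is precision, and protection against an observed imbalance, in a study whose purpose is estimation.

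For an assumed 10-50% PDI share, an assumed 0.5 SD route difference and unstratified allocation, the typical shift at 18/20 is 16-26% of d=0.32. The 30-50% figure is the 95% extreme, not the expected shift. If few or no women entered by PDI, the route component is small or nil. Adjusting for route alone gains little; most of the gain would come from the Day 1 score, by an amount that depends on a correlation the documents do not give.

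**What to change.** 1. Estimate the drug effect with the protocol's mixed model, with entry route as a fixed factor beside Drug. For EPDS, MIBS and BSI, adjust for the Day 1 score of the same scale. PCL-5 and PBQ have no Day 1 score, so use another one there, such as EPDS or PDI. Use only scores taken before the first dose; section 5.1.2 lists questionnaires and first dose together without fixing their order.
2. Include route in the imputation model and list the variables imputed. If Assessment 1 scales were among them, leave those of Day 1 entrants out of the imputation and out of the 18.59% figure.
3. Report numbers by route and arm, and state whether the schedule was stratified by route.
4. Label the adjusted analysis as added after data collection, because the SAP already reports results on collected data, and show it beside the Mann-Whitney results.

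The cost is SAP wording, a rerun, and one or two degrees of freedom; entry route should be on record for every woman. The drawback is a poorly estimated route term if few women entered by PDI (about 4 of 38 at a 10% share). In that case, report the model with the Day 1 score alone as well.
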